7.3 VITAL SIGNS, 12-LEAD ECG, PHYSICAL AND NEUROLOGICAL EXAMINATIONS, AND C-SSRS

7.3.1 Vital Signs

Vital signs include temperature, blood pressure, pulse rate, respiration rate, height, weight and BMI.

All vital signs will be presented in Système International (SI) units. Quantitative results (including actual value, and change from baseline to each post-baseline visit) will be summarized using descriptive statistics by post-baseline time point for each parameter.

Listings of vital signs with abnormal flags will be provided.

7.3.2 12-Lead ECG

12-lead ECG data will be reported in listing.

7.3.3 Physical and Neurological Examinations

Physical examination data will be summarized using descriptive statistics by post-baseline visit, for each component. Listings for physical examination will be provided.

Neurological examination data will be reported in listing.

7.3.4 C-SSRS

C-SSRS data will be summarized and listed for each question by visit.

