- c. Status epilepticus at any time during the clinical investigation.
- d. Any Suicidal Behavior as classified by the Columbia Suicide Severity Rating Scale (C-SSRS) or a "yes" answer to questions 4 and 5 in the Suicidal Ideation section of the C-SSRS. These patients should be referred to psychiatric evaluation immediately.

11. Any subject who has the following liver enzyme findings should be immediately contacted and instructed to stop the study drug or start immediate down titration of the study drug

- a. ALT or AST $> 8 \times$ ULN
- b. ALT or AST $> 5 \times$ ULN for more than 2 weeks
- c. ALT or AST $> 3 \times$ ULN and total bilirubin $> 2 \times$ ULN
- d. ALT or AST $> 3 \times$ ULN with the appearance of fatigue, nausea, vomiting, right upper quadrant pain or tenderness, fever, rash or eosinophilia

Patients with ALT or AST $> 3 \times$ ULN but $\leq 8 \times$ ULN and no clinical signs or symptoms indicating liver dysfunction can, at the discretion of the investigator, continue the intake of study drug with close monitoring.

All patients who fall into either category (patients who must discontinue the study drug [a, b, c, and d] and who may continue the study drug with close monitoring) must be brought back to the study center without any delay, the next day if possible, but no later than 72 hours after the study results have been received, for evaluation of the underlying cause and confirmatory laboratory testing. More frequent monitoring of the liver tests should be initiated.

Discontinuation decisions will be made at each participating site by the Site Principal Investigator. If feasible, the process of discontinuation should be discussed with the Medical Monitor. The decisions regarding the discontinuation of the investigational therapy, whether the study medication should be stopped immediately or tapered should be discussed with the Medical Monitor, but final decisions about the process will remain at the discretion of the Site Principal Investigator.

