12.6 Appendix 6: Columbia Suicide Severity Rating Scale (C-SSRS) Since Last Visit

Translations in Bulgarian, German, Polish and Russian are available upon request.

COLUMBIA-SUICIDE SEVERITY RATING SCALE (C-SSRS)

Since Last Visit

Version 1/14/09

***Posner, K.; Brent, D.; Lucas, C.; Gould, M.; Stanley, B.; Brown, G.; Fisher, P.; Zelazny, J.;
Burke, A.; Oquendo, M.; Mann, J.***

Disclaimer:

This scale is intended for use by trained clinicians. The questions contained in the Columbia-Suicide Severity Rating Scale are suggested probes. Ultimately, the determination of the presence of suicidality depends on clinical judgment.

Definitions of behavioral suicidal events in this scale are based on those used in ***The Columbia Suicide History Form***, developed by [name] and [name], Conte Center for the Neuroscience of Mental Disorders (CCNMD), New York State Psychiatric Institute, [name]. (Oquendo M. A., Halberstam B. & Mann J. J., Risk factors for suicidal behavior: utility and limitations of research instruments. In M.B. First [Ed.] Standardized Evaluation in Clinical Practice, pp. 103 -130, 2003.)

For reprints of the C-SSRS contact [name]., New York State Psychiatric Institute, [name]; inquiries and training requirements contact [contact]

SUICIDAL IDEATION		Since Last Visit																		

Ask questions 1 and 2. If both are negative, proceed to "Suicidal Behavior" section. If the answer to question 2 is "yes," ask questions 3, 4 and 5. If the answer to question 1 and/or 2 is "yes", complete "Intensity of Ideation" section below.
 
1. Wish to be Dead Subject endorses thoughts about a wish to be dead or not alive anymore, or wish to fall asleep and not wake up. Have you wished you were dead or wished you could go to sleep and not wake up?
 
If yes, describe:
			
Yes  No 
																	

2. Non-Specific Active Suicidal Thoughts General, non-specific thoughts of wanting to end one's life/commit suicide (e.g. "I've thought about killing myself") without thoughts of ways to kill oneself/associated methods, intent, or plan during the assessment period. Have you actually had any thoughts of killing yourself?
 
If yes, describe:
		
Yes  No 
																		

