2. STATISTICAL METHODS

2.1 GENERAL CONSIDERATIONS

In general, continuous variables will be summarized by number of subjects, mean, standard deviation (SD), median, minimum, and maximum values. Categorical variables will be summarized by counts and percentage of subjects in each category. If data is sparse, no summary table will be presented. Summary tables will present data by treatment received during the this study, i.e. Ganaxolone. Source data for the summary tables and statistical analyses will be presented as subject data listings, which include data collected on the electronic case report forms (eCRFs) as well as any derived variables for all enrolled subjects.

Baseline seizure activity will be determined by 8 weeks of retrospective recording in subject daily seizure calendars in Study 1042-0603.

Baselines for safety assessments are defined as the last non-missing value of the assessment before the first dose of treatment in Study 1042-0603.

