2.5 HANDLING OF MISSING DATA

Unless otherwise specified, missing data will not be imputed. All analyses will be based on available data.

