7. SAFETY ANALYSIS

All safety analyses will be performed by treatment, i.e. Ganaxolone, in the Safety Population. Safety assessments include:

- AE
- Clinical laboratory tests
- Vital signs including temperature, blood pressure, pulse rate, and weight
- 12-lead ECG
- Physical and neurological examinations
- Columbia-Suicide Severity Rating Scale (C-SSRS)

Baseline is defined as the last non-missing value obtained before the first treatment in the preceding Study 1042-0603.

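### The C-SSRS is tabulated only by question and visit, so no planned table gives the number of subjects with any suicidal ideation or behaviour on study

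*SAP*

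**What the plan says.** SAP 7.3.4 is a single sentence: "C-SSRS data will be summarized and listed for each question by visit". SAP 1.2.1 and 7 list the C-SSRS among the safety endpoints, and SAP 9 confirms that it is reported as one. Safety and tolerability are the primary objective.

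Four general rules bear on how that sentence would be carried out:

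- SAP 2.1: "Categorical variables will be summarized by counts and percentage of subjects in each category". No denominator is given. The same section drops the summary table when data are sparse.
- SAP 2.5: "Unless otherwise specified, missing data will not be imputed. All analyses will be based on available data".
- SAP 7: "All safety analyses will be performed by treatment, i.e. Ganaxolone, in the Safety Population".
- SAP 2.3: tables use scheduled visits, unscheduled visits appear only in listings, and no analysis windows are built.

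The instrument in Protocol Appendix 6 is the version that covers the time since the last visit. Its ideation section begins "Ask questions 1 and 2. If both are negative, proceed to" the behaviour section; questions 3 to 5 follow only a positive answer to question 2. The Schedule of Events places the scale at V1 and at V2 to V8, and its footnote 4 allows other procedures at unscheduled visits as needed. Protocol 8.3.4.1, item 10d, makes C-SSRS findings a reason for immediate withdrawal.

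**The concern.** The safety question is how many subjects had suicidal ideation or behaviour at any time during treatment, and how severe it was at worst. A visit-by-visit table of a form with a short recall period does not answer it. Each row covers a different interval, the same subject may or may not appear in several rows, and the rows cannot be combined without subject-level data. A positive finding at an unscheduled visit is in no row at all.

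The V7 row has a further weakness. Protocol 8.3.4.2 sends early terminators through the Visit 7 procedures, and no analysis windows are built. That row can therefore mix completers at Week 104 with subjects who left much earlier.

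The SAP does define a once-per-subject count for adverse events (SAP 7.1). It has no equivalent for the C-SSRS. A smaller matter is that questions 3 to 5 are blank by design whenever question 2 is negative, and nothing says whether those blanks count as negative or fall out of the denominator.

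**Working it through.** The documents state no C-SSRS rate and no number assessed, so there is no figure to reproduce. Every rate and count below is an assumption chosen for illustration.

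**1. Can the by-visit rows give the ever-positive count?**

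Inputs: seven scheduled assessments after entry, V2 to V8 (Schedule of Events); an assumed rate p positive at each visit; for simplicity, the same subjects assessed at all seven.

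- Lower limit, the same subjects positive every time: p.
- Upper limit, different subjects at every visit: 7 × p.
- Visits independent: 1 − (1 − p)^7.

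| Assumed p per visit | Same subjects | Independent | Different subjects |
|---|---|---|---|
| 1% | 1.0% | 1 − 0.99^7 = 6.8% | 7 × 1% = 7.0% |
| 2% | 2.0% | 1 − 0.98^7 = 13.2% | 7 × 2% = 14.0% |
| 3% | 3.0% | 1 − 0.97^7 = 19.2% | 7 × 3% = 21.0% |

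One set of by-visit rows is thus compatible with a sevenfold range in the share ever positive. Positives found at unscheduled visits would come on top, and they are in none of the rows.

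**2. Does another planned table supply the count?**

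- SAP 7.1 counts subjects by preferred term for treatment-emergent events. Nothing in the documents as supplied requires a positive C-SSRS answer to be entered as an adverse event.
- SAP 3.1 tabulates reasons for discontinuation. It does not say that suicidality is a category of its own, and ideation below the withdrawal threshold would not appear.
- SAP 7.3.4 provides a listing, which is not a summary.

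No section defines a composite of any ideation or any behaviour, a worst category after entry, or a shift from baseline.

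**3. What could the denominator for questions 3 to 5 be?**

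Suppose 4 subjects answer yes to question 2 at a visit and 2 of them answer yes to question 4.

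- Only those asked: 2/4 = 50.0%.
- All assessed at the visit: 2/30 = 6.7%, 2/100 = 2.0%, or 2/350 = 0.6%. The last uses the protocol's approximate maximum enrolment.

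SAP 2.5 could be taken to support the first reading, because a skipped item holds no available data. SAP 7 points towards the Safety Population. SAP 7.3.4 does not choose.

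**The case against.** The strongest reply is that this is a small, single-arm, descriptive study. SAP 9 says it ended early with few patients, and all C-SSRS data will be listed. A reader can count ever-positive subjects by hand. Counts appear beside percentages, so nobody need be misled by a percentage taken over two people, and the sparse-data rule may remove such a row anyway. For the gravest findings, immediate withdrawal under item 10d means that few subjects could be positive at several visits, so summed counts should lie close to subject counts.

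Much of this stands. It limits the harm, and it makes the problem larger for lower-level ideation than for behaviour. It does not supply the result. A hand count from a listing is not a prespecified summary of a safety endpoint. The sparse-data rule could also remove the by-visit table itself, leaving no C-SSRS summary at all. SAP 8.2 provides for no data and safety monitoring board that might have made a subject-level review.

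A reader might go further and infer that percentages for questions 3 to 5 will be taken over only the subjects asked, so that the table will grossly overstate ideation with intent or plan. The documents do not support that. They leave the denominator open, items skipped by design are not plainly missing data, and SAP 7 names the Safety Population. The 50% above is one possible reading and not the planned result.

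**Conclusion.** The point holds as a reporting gap. SAP 7.3.4 yields no count of subjects with any suicidal ideation or behaviour after entry, and no other planned table fills that place. On the assumed rates, the by-visit rows leave the ever-positive share uncertain by up to a factor of seven: 1% to 7% at 1% per visit, and 2% to 14% at 2%. These ranges assume equal rates and the same subjects assessed at all seven visits. Attrition would change the figures but would not make the rows sufficient.

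The denominator for questions 3 to 5 is a secondary point of missing detail. It is undefined, not shown to be wrong. Neither matter affects trial conduct, and the listings and adverse event tables soften the consequence. Because safety is the primary objective and the remedy is cheap, the SAP should be changed.

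**What to change.** Keep the by-visit table and add two things to SAP 7.3.4.

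1. **A by-subject table that counts each subject once.** The denominator is Safety Population subjects with at least one C-SSRS after entry, whether at a scheduled, early-termination or unscheduled visit. Show n (%) who ever had (i) any ideation, questions 1 to 5; (ii) ideation at question 4 or 5; (iii) any suicidal behaviour. Category (ii) is for reporting only and does not interpret item 10d. Add the worst ideation category after entry against a named reference. That reference is either the SAP safety baseline, taken before first treatment in Study 1042-0603, or the level at entry, which is the Visit 10 value held in the 1042-0603 database (Schedule of Events, footnote 3). State an exception to SAP 2.3 so that unscheduled assessments count in this table, and an exception to the sparse-data rule so that the table is always produced.
2. **A denominator rule for the by-visit table.** Use all subjects with a C-SSRS at that visit, and count questions 3 to 5 as No when they were skipped because question 2 was No.

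The cost is SAP wording, one extra table and, if the entry level is chosen, a merge with existing 1042-0603 data. No new data collection is needed.

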8. INTERIM ANALYSES AND DATA AND SAFETY MONITORING BOARD (DSMB)

8.1 INTERIM ANALYSES

No formal interim analyses are planned.

8.2 DATA AND SAFETY MONITORING BOARD (DSMB)

DSMB is N/A.

9. SUMMARY OF MAJOR CHANGES IN THE PLANNED ANALYSES

Below changes from protocol have been made in the SAP.

Safety Endpoints:

Due to early termination of the study and low patient numbers 12-lead ECG and Neurological Examination results will only be reported in listings. C-SSRS data were collected in eCRF and will be reported as one of the safety endpoints.

Efficacy Endpoints:

Due to early termination of the study and low patient numbers seizure free intervals and seizure free days will not be derived and the Clinician's Global Impression of Improvement, and the Patient/Caregiver Global Impression of Improvement results will only be reported in listings

To avoid confusion, protocol defined primary and secondary efficacy endpoints are re-named as main and other efficacy endpoints, respectively, to clarify that the primary objective of the study is to assess the safety and tolerability of adjunctive ganaxolone during two-year open-label treatment in adult subjects with drug-resistant partial-onset seizures.
